5.0 Analysis Populations

5.1 Analysis Datasets

Intent-to-Treat (ITT) Dataset

The intent-to-treat (ITT) dataset will include all randomized subjects who receive any dose of study drug infusion. The data from the ITT dataset will be analyzed by the treatment group assigned at the time of randomization, even if the subject does not receive the correct treatment, is not compliant with the protocol or does not follow through with the study until completion. All efficacy analyses will be conducted on the intent-to-treat dataset unless otherwise specified.

Safety Dataset

The safety dataset will include all randomized subjects who received at least one dose of study drug infusion. For this analysis dataset, actual treatment received instead of treatment assignment at the time of randomization will be used. All safety analyses will be conducted on the safety dataset unless otherwise specified.

5.2 Variables Used for Stratification of Randomization

Subject randomization is stratified by study site except for Japanese subjects who are randomly assigned to three groups with 1:1:1 ratio within Japan.

6.0 Analysis Conventions

6.1 Statistical Significance

Unless otherwise specified, statistical tests will be two-sided for efficacy and safety analyses. The null hypotheses for efficacy will be rejected at the pre-specified significance level with the overall Type I family wise error rate (FWER) to be controlled at the two-sided 5% level (including type I error rate spent in interim analyses). *P* values will be rounded to five decimal points for primary and key secondary variables included in the FWER control and rounded to three decimal points for other analyses before assessing statistical significance. Multiplicity adjustment will be carried out to control the overall FWER rate in this study.

6.2 Visit Definitions

Definition of Rx Day (Days Relative to the First Dose of Study Drug)

Rx Day is calculated for each time point as the number of days between the day of the first dose of study drug and the specific time point. For dates before the first dose date of study drug, Rx day = date of time point – first dose date; for dates on or after the first dose date of study drug, Rx day = date of time point – first dose date + 1. Thus, Rx Day is a negative value when the time point of interest is prior to the first study drug dose day; Rx Day is a positive value when the time point of interest is on or after the first study drug dose day. There is no Rx Day 0. With this defined algorithm, the day of the first dose of study drug will be Rx Day 1.

RxEnd Day is calculated for each post-treatment time point as the number of days between the day of the last dose of study drug and the specific time point:
RxEnd Day = date of time point – last dose date. With this defined algorithm, the day of the last dose of study drug will be RxEnd Day 0.

Definition of Baseline and Final Observation

Unless otherwise specified, for all efficacy analyses and for all safety analyses of the double-blind Treatment Period, "baseline" shall refer to the last non-missing observation prior to the first dose of study drug and "final" for the double-blind Treatment Period shall refer to the last non-missing observation no more than 45 days after the last dose of the study drug for both efficacy variables and safety variables. The "final" for the post-treatment follow-up period for safety variables shall refer to the last non-missing observation greater than 45 days but no more than 20 weeks after the last dose of study drug.

Randomization and study drug administration are the last activities of the Day 1 Visit after the site completes other study procedures and verifies that the subject is eligible to participate in the study. From the definition of "baseline," it is clear that a baseline for a specific measurement is the last non-missing observation taken up to and on the Day 1 Visit (the Randomization Visit). At the computation level, the value of "baseline" for an efficacy or safety assessment is determined using the Rx Day associated with the visit. Namely, baseline value is determined by taking the last non-missing observation obtained before the time of first dosing on Rx Day 1. If an SAE occurs on the first dosing day, the event will be reported as a post baseline event and the related safety assessments will be considered post-baseline data as well.

Definition of Analysis Windows

To perform longitudinal data analysis, observations that are obtained after the first day of study drug administration will be assigned to an analysis "week" associated with the Rx Days that are corresponding to the observations. Unless otherwise specified, efficacy observations and safety observations no more than 45 days after the last dose of study drug will be included in analyses for the double-blinded period. Safety observations later than 45 days, but no more than 20 weeks, after the last dose of study drug will be included for the post-treatment follow-up period safety analysis. The intervals presented below for

each schedule visit (Rx Days X through Y) include both Rx Days X and Y. The nominal day for each scheduled visit is defined in "Activities" row in [Table 2](#).

For measurements that are planned to be collected during double-blind treatment period at Weeks 12, 24, 36, and 52, i.e., PSPRS, SEADL, PGI-C, PSP-QoL and UPDRS Part II, observations will be mapped to an analysis "week" according to the following windows defined by Rx day.

- Week 12 Rx Days 2 through 126
- Week 24 Rx Days 127 through 210
- Week 36 Rx Days 211 through 308
- Week 52 Rx Days > 308

For measurements that are planned to be collected during double-blind treatment period at Weeks 8, 20, 32, and 48, i.e., RBANS, Color Trails Test (Parts 1 & 2), letter fluency, EQ-5D, and NNIPPS-PPS, observations will be mapped to an analysis "week" according to the following windows defined by Rx day.

- Week 8 Rx Days 2 through 98
- Week 20 Rx Days 99 through 182
- Week 32 Rx Days 183 through 280
- Week 48 Rx Days > 280

For measurements that are planned to be collected during double-blind treatment period at Weeks 8, 12, 20, 24, 32, 36, 48 and 52, i.e., CGI-S and CGI-C, observations will be mapped to an analysis "week" according to the following windows defined by Rx day.

- Week 8 Rx Days 2 through 70
- Week 12 Rx Days 71 through 112
- Week 20 Rx Days 113 through 154
- Week 24 Rx Days 155 through 196
- Week 32 Rx Days 197 through 238

- Week 36 Rx Days 239 through 294
- Week 48 Rx Days 295 through 350
- Week 52 Rx Days > 350

For measurements that are planned to be collected during double-blind treatment period at Weeks 1, 2, 4, 8, 12, 13, 14, 16, 20, 24, 28, 32, 36, 40, 44, 48 and 52, i.e., vital sign and C-SSRS observations will be mapped to an analysis "week" according to the following windows defined by Rx day. The first 30 randomized subjects represent Cohort 1 and the rest randomized subjects represent Cohort 2.

- Week 1 Rx Days 2 through 10 (Cohort 1 and Cohort J1 only)
- Week 2 Rx Days 11 through 22 (Cohort 1 and Cohort J1 subjects)
Rx Days 2 through 22 (Cohort 2 subjects)
- Week 4 Rx Days 23 through 42
- Week 8 Rx Days 43 through 70
- Week 12 Rx Days 71 through 87 (Cohort 1 and Cohort J1 subjects)
Rx Days 71 through 98 (Cohort 2 subjects)
- Week 13 Rx Days 88 through 94 (Cohort 1 and Cohort J1 only)
- Week 14 Rx Days 95 through 105 (Cohort 1 and Cohort J1 only)
- Week 16 Rx Days 106 through 126 (Cohort 1 and Cohort J1 subjects)
Rx Days 99 through 126 (Cohort 2 subjects)
- Week 20 Rx Days 127 through 154
- Week 24 Rx Days 155 through 182
- Week 28 Rx Days 183 through 210
- Week 32 Rx Days 211 through 238
- Week 36 Rx Days 239 through 266
- Week 40 Rx Days 267 through 294
- Week 44 Rx Days 295 through 322
- Week 48 Rx Days 323 through 350
- Week 52 Rx Days > 350

For measurements that are planned to be collected during double-blind treatment period at Weeks 2, 4, 8, 12, 16, 20, 24, 28, 32, 36, 40, 44, 48, and 52, i.e., body weight observations will be mapped to an analysis "week" according to the following windows defined by Rx day.

- Week 2 Rx Days 11 through 21
- Week 4 Rx Days 22 through 42
- Week 8 Rx Days 43 through 70
- Week 12 Rx Days 71 through 98
- Week 16 Rx Days 99 through 126
- Week 20 Rx Days 127 through 154
- Week 24 Rx Days 155 through 182
- Week 28 Rx Days 183 through 210
- Week 32 Rx Days 211 through 238
- Week 36 Rx Days 239 through 266
- Week 40 Rx Days 267 through 294
- Week 44 Rx Days 295 through 322
- Week 48 Rx Days 323 through 350
- Week 52 Rx Days > 350

For measurements that are planned to be collected during double-blind treatment period at Weeks 2, 4, 8, 12, 24, 48, and 52, i.e., clinical laboratory tests will be mapped to an analysis "week" according to the following windows defined by Rx day.

- Week 2 Rx Day 2 through 21 (Cohort J1 only)
- Week 4 Rx Day 22 through 42 (Cohort J1 only)
Rx Day 2 through 42 (Cohort 1 only)
- Week 8 Rx Day 43 through 70 (Cohort 1 and Cohort J1 only)
- Week 12 Rx Days 71 through 126 (Cohort 1 and Cohort J1 subjects)
Rx Days 2 through 126 (Cohort 2 subjects)

- Week 24 Rx Days 127 through 252
- Week 48 Rx Days 253 through 350
- Week 52 Rx Days > 350

For measurements that are planned to be collected during double-blind treatment period at Weeks 1, 2, 4, 8, 12, 24, 36 and 52, i.e., ECG observations will be mapped to an analysis "week" according to the following windows defined by Rx day.

- Week 1 Rx Days 2 through 10 (Cohort 1 and Cohort J1 only)
- Week 2 Rx Days 11 through 21 (Cohort 1 and Cohort J1 only)
- Week 4 Rx Days 22 through 42 (Cohort 1 and Cohort J1 subjects)
Rx Days 2 through 42 (Cohort 2 subjects)
- Week 8 Rx Days 43 through 70
- Week 12 Rx Days 71 through 126
- Week 24 Rx Days 127 through 210
- Week 36 Rx Days 211 through 308
- Week 52 Rx Days > 308

For measurements that are planned to be collected during double-blind treatment period at Weeks 2, 12, 24, and 52, i.e., brain volumetric MRI observations will be mapped to an analysis "week" according to the following windows defined by Rx day.

- Week 2 Rx Days 2 through 49 (Cohort 1 and Cohort J1 only)
- Week 12 Rx Days 50 through 126 (Cohort 1 and Cohort J1 subjects)
Rx Days 2 through 126 (Cohort 2 subjects)
- Week 24 Rx Days 127 through 266
- Week 52 Rx Days > 266

For vital sign measurements and C-SSRS assessments that are planned to be collected during post-treatment follow-up period on Weeks 60 and 68, observations will be mapped to an analysis "week" according to the following windows defined by RxEnd day.

- Post-Treatment Week 12 RxEnd Days 46 through 112
- Post-Treatment Week 20 RxEnd Days > 112

For ECG measurements that are planned to be collected during post-treatment follow-up period at Weeks 60, observations will be mapped to an analysis "week" according to the following windows defined by RxEnd day.

- Post-Treatment Week 12 RxEnd Days > 45

If more than 1 observation is included in a visit time window, the observation that is closed to the nominal day of the visit will be used in the analysis. If two observations have the same distance to the nominal day of the visit, the last non-missing observation will be used in analyses. If more than 1 observation occurs on the same day, the average will be calculated and used in analyses.

7.0 Demographics, Baseline Characteristics, Subject History, and Previous/Concomitant Medications

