5.0 Investigational Plan

5.1 Overall Study Design and Plan: Description

This Phase 2, randomized, double-blind, placebo-controlled, multiple dose, multicenter study will consist of a screening period of up to 8 weeks (56 days), a 52 week double-blind treatment period, and a post-treatment follow-up period of approximately 20 weeks following last study drug administration (including those subjects who prematurely discontinue from treatment, decline to participate in or do not qualify for participation in a long term extension [LTE] study). The study is planned to be conducted at approximately 60 sites around the world. Approximately 330 subjects will participate in the study.

At the end of the treatment period, eligible subjects who completed the 52 week treatment period may enter a separate LTE study for extended treatment. All activities for the LTE study will be outlined in a separate extension study protocol.

Eligible subjects will be enrolled into the Treatment Period of the study on Day 1 and receive their first infusion of study drug. During the first 4 weeks, subjects will have 3 study drug infusions; the first on Day 1, the second at Day 15, and the third at Day 29; thereafter, subjects will return to the study site every 28 Days for their study drug infusion, blood collection, study procedures and assessments as outlined in the Study Activities Table ([Appendix C](#)). This dosing schedule (with one additional dose delivered at Day 15) will enable rapid attainment of steady-state drug levels in plasma to maximize the likelihood of demonstrating a treatment effect. Subjects will be observed on-site for at least 2 hours following each of the first 4 infusions of study drug and for at least 30 minutes after the end of infusion of all doses thereafter.

Refer to Section [5.5.1](#) for details on infusion times.

Approximately 330 subjects with PSP matching the selection criteria described in Section [5.2](#), will be eligible to enter the study double-blind treatment period. Eligible subjects will be randomized to one of the two ABBV-8E12 dose arms (2000 mg or 4000 mg) or placebo in a 1:1:1 ratio. Doses will be administered via IV infusion at Day 1,

Day 15, Day 29, and every 28 days thereafter through dose 14 at Week 48. Refer to Section 5.5.1 for details on infusion times.

Safety and tolerability will be monitored throughout the study.

The study will consist of 3 Cohorts (Table 1).

Table 1. Description of Cohorts

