- a. All screening assessments are to be completed within -56 to -8 days prior to initial study drug administration (Day 1). Refer to Table 7 for a pre-defined order of administration that should occur during each visit. Screening visit assessments may be completed on a single date or multiple visit days. Screening is complete when all screening assessments are complete or subject screen fails. If screening assessments are completed on a single date, the scales for Screening Visit 1 (SV1) will be performed in the recommended order in this table, followed by the recommended order of scales for Screening Visit 2 (SV2). Also, the CGI-S and the C-SSRS will only be performed once.
- b. Visits on Days 5, 15, 89, and 99 must be scheduled within ± 2 days. Visits on all other days may be scheduled within ± 4 days. The scheduled date for each study visit will be based on the number of days from the beginning of the treatment period on study Day 1, as indicated in the Study Activities table.
- c. Audio recordings/central review of the administration/assessment of selected scales may be conducted.
- d. Study-related assessments, procedures or activities may not occur prior to subject completing the signed informed consent process. If at any time during the study, a subject experiences diminished decision-making capacity, a legally authorized representative (LAR) is necessary when an informed consent must be obtained.
- e. Update medical and/or neurological history with any findings prior to randomization.
- f. Additional symptom-driven physical examinations can be performed as needed.
- g. All systolic and diastolic blood pressure and pulse rate measurements are to be measured as part of an orthostatic assessment. An attempt should be made to obtain all vital sign measurements at the same time of day and using the same arm.
- h. Height will be collected at the screening Visit 1 only. On dosing days, weight will be collected prior to the start of the infusion.
- i. All females of child-bearing potential must have a negative serum pregnancy test performed at screening and Premature Discontinuation. A negative urine pregnancy test result is required prior to any radiological procedures involving exposure to radiation.
- j. A detailed description for ECG parameters and schedule can be found in Section 5.3.1.1.

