11.0 Safety Analysis

11.1 General Considerations

All safety analyses will be performed on the safety dataset. Treatment group differences in safety parameters are evaluated using two-sided test at the significance level of 0.050. When statistical tests are performed, the comparisons will be between each ABBV-8E12 dose and placebo. With the exception of adverse events, all safety assessments that are taken no more than 45 days after the last dose of study drug will be included in the safety evaluation of the Double-blind Treatment Period. All safety assessments that are taken more than 45 days but no more than 20 weeks after the last dose of study drug will be included in the safety evaluation for the Post-Treatment Follow-Up Period.

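### The SAP's 20-week limit on post-treatment safety data falls on the nominal day of the Week 68 visit, so a protocol-compliant visit can be excluded, against the SAP's own open-ended window and Protocol 8.1.6

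*SAP*

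**What the plan says.** **The limit.** The SAP sets the same upper bound in three places.
- SAP 6.2, analysis windows: "Safety observations later than 45 days, but no more than 20 weeks, after the last dose of study drug will be included" in the post-treatment follow-up analysis.
- SAP 6.2, final post-treatment value: the last non-missing "observation greater than 45 days but no more than 20 weeks after the last dose of study drug".
- SAP 11.1: "All safety assessments that are taken more than 45 days but no more than 20 weeks after the last dose of study drug" go to the follow-up evaluation. Adverse events are handled separately.

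**The day count.** SAP 6.2 defines "RxEnd Day = date of time point – last dose date", so the limit is RxEnd Day 140, with Day 140 itself included.

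**The schedule.** Protocol 5.1 doses "every 28 days thereafter through dose 14 at Week 48", which Appendix C places on Day 337. The last follow-up visit is Week 68. Appendix C, footnote b, says "Visits on all other days may be scheduled within ± 4 days", apart from four named early visits, and counts every visit date from Day 1 rather than from the last dose.

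**The mapping window.** For post-treatment vital signs and C-SSRS, SAP 6.2 lists "Post-Treatment Week 20 RxEnd Days > 112", with no upper end.

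**The protocol rule.** Protocol 8.1.6 assigns safety assessments up to 20 weeks after the last dose to the double-blind period and later ones to the Post-treatment Follow-up Period. It sets no point after which data are dropped. SAP 14.0, which lists changes from the protocol, does not mention this rule.

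**The concern.** A limit on admissible data should sit clear of the last scheduled visit. Here it coincides with that visit's nominal day. A subject seen one day after the nominal day is within the protocol's visit window, yet under the three limit statements the data belong to neither SAP analysis period. A subject seen one day earlier is kept. That subject-level difference has no scientific basis.

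The SAP is also not consistent with itself. A programmer who applies the limit and one who applies the open-ended mapping window would build different datasets for the same visit.

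At stake are the Week 68 vital signs in the change-from-double-blind summaries (SAP 11.3.1 and 11.4.1) and the Week 68 row of the C-SSRS summary (SAP 11.6.1). Where the visit is excluded, the final post-treatment vital signs fall back to Week 60.

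**Working it through.** **1. Inputs.** Last scheduled dose: Day 337 (Appendix C). Weeks 60 and 68: the documents' own convention, Week 48 = 48 × 7 + 1 = Day 337, gives 60 × 7 + 1 = Day 421 and 68 × 7 + 1 = Day 477. Visit window: ±4 days for each. Limit: 20 × 7 = 140 days.

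**2. Reproduce the SAP's own boundary.** RxEnd Day for Week 60 = 421 − 337 = 84. RxEnd Day for Week 68 = 477 − 337 = 140. Midpoint = (84 + 140)/2 = 112, which is the SAP's boundary between its two post-treatment windows. The SAP's windows therefore agree with a nominal Week 68 visit on RxEnd Day 140, the same day as the limit.

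**3. Range of compliant visits.** Let d be the shift of the Week 48 dose and v the shift of the Week 68 visit, each from −4 to +4. The interval is 140 + v − d.
- Dose exactly on Day 337: Days 136 to 144.
- Both free to move: Days 132 to 148.

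The visit is beyond the limit whenever v > d, that is, on Days 141 to 148.

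**4. Share excluded.** The documents give no distribution of visit dates, so this is a range under stated assumptions. If the interval is spread symmetrically about Day 140, and p is the share exactly on that day, the excluded share is (1 − p)/2.

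| Assumption | p | Excluded |
|---|---|---|
| All on the day | 1 | 0% |
| 80% on the day | 0.8 | 10% |
| Half on the day | 0.5 | 25% |
| Visit uniform over ±4, dose on Day 337 | 1/9 | 4/9 = 44% |
| Visit and dose both uniform over ±4 | 9/81 | 36/81 = 44% |

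A symmetric spread cannot exceed 50%. An asymmetric one can. With the dose on Day 337 and visit weights 5 − v (leaning early), the share is 10/45 = 22%. With weights 5 + v (leaning late), it is 30/45 = 67%.

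**5. What a later limit would do.** At Day 144, nothing is lost if the dose is on Day 337, but 10/81 = 12% is lost if both dates are uniform. At Day 148, nothing is lost in either case.

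**6. A missed last dose.** If the last dose was Week 44 (Day 309) and Week 68 stays on the Day 1 schedule, the interval is nominally 477 − 309 = 168 days, or 160 to 176 with both windows. Every such visit is beyond Day 140, and also beyond Day 148.

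**The case against.** **The open-ended window may already keep the data.** If the specific mapping rule governs, nothing is lost. This is possible but not settled. The SAP leaves other last windows open as well, such as Week 52 for the PSPRS, and relies on the 45-day rule to close them. On that pattern the 20-week limit would close this window too. Either way, the text needs correcting.

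**The exposure is narrow.** This stands.
- Treatment-emergent adverse events count by date of onset or worsening (SAP 11.2), so an event that began within 20 weeks counts even if reported at a late visit.
- Post-treatment ECG is planned at Week 60 only.
- Counts of potentially clinically significant vital signs use double-blind observations, and the listing covers the whole study (SAP 11.4.2).
- C-SSRS is also summarised over the whole study, so the by-visit row is the part clearly exposed.
- Only subjects who do not enter the extension have these visits (Protocol 5.1).

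**Week 68 is not the only late look.** This stands. A reader might infer that it is the sole measurement after most of the antibody has gone, but vital signs and C-SSRS are also taken at Week 60. With the half-life of 27 to 37 days in Protocol 3.0, Week 60 is 84/37 = 2.3 to 84/27 = 3.1 half-lives after the last dose, by which time about 79% to 88% is eliminated. Week 68 is 3.8 to 5.2 half-lives out.

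**The primary safety objective is worded for up to 52 weeks.** This also stands: Week 68 data support that objective but are not its core.

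**Conclusion.** The point holds as an inconsistency that can change which data are analysed. On the completer schedule the limit coincides with the nominal Week 68 visit, and compliant visits on RxEnd Days 141 to 148 fall outside both SAP periods if the limit is applied. That contradicts the SAP's own mapping window and departs, without a record in SAP 14.0, from Protocol 8.1.6.

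A reader might infer that close to half of final safety visits would be discarded. The documents do not support that. The 44% rests on assumed uniform visit days; a symmetric spread gives 10% to 25% if 80% to 50% of visits are on the day. Nor is the whole visit lost: the effect is mainly on post-treatment vital-sign changes, including the final value, and on the by-visit C-SSRS summary. The percentages also do not describe early discontinuers, whose last dose is not on Day 337 and whose follow-up is only approximately 20 weeks. It would likewise be wrong to say that such visits have no place under the protocol; the gap is in the SAP.

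The consequence is modest, but the correction is worth making because it is specific and nearly free.

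**What to change.** In both SAP 6.2 statements (final post-treatment value and analysis windows) and in SAP 11.1, remove the 20-week upper limit for post-treatment safety assessments other than adverse events. Include all assessments more than 45 days after the last dose through the Week 68 visit. This agrees with the open-ended window in SAP 6.2 and with the inclusion of later data in Protocol 8.1.6.

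If a numeric limit is preferred, set it no lower than RxEnd Day 148, close the last mapping window at the same day, and add a rule that the scheduled Week 68 visit is kept for subjects whose last dose was before Week 48. Day 148 alone would still exclude a subject who missed Dose 14 (nominally Day 168).

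Leave the treatment-emergent adverse event definition at 20 weeks. Record the change in SAP 14.0, and note there that the SAP divides the two periods at 45 days where Protocol 8.1.6 divides them at 20 weeks.

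The cost is a few sentences in the SAP and one condition in the programs. No new data, visits or protocol amendment are required.

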(normal/abnormal) with the central ECG laboratory in case of relevant divergent assessments and reconcile as he/she determines is appropriate.

ECGs will be collected as single ECGs as follows:

Cohort 1 and Cohort J1 Subjects:

- **Screening**
 - May be done at any time during the visit.
- **Day 1 (Dose 1)**
 - Pre-dose (just prior to pre-infusion PK sample collection and the start of infusion) and within 15 minutes after the end of infusion prior to the PK sample collection
- **Day 5**
 - Collection should be scheduled as close as possible to the corresponding time of the post infusion collection on Day 1.
- **Day 15 (Dose 2)**
 - Pre-dose (just prior to the start of infusion) and within 15 minutes after the end of infusion prior to the PK sample collection
- **Days 29 and 57 (Doses 3 and 4)**
 - Pre-dose (just prior to the start of infusion)
- **Day 85 (Dose 5)**
 - Pre-dose (just prior to the start of infusion) and within 15 minutes after the end of infusion (prior to the PK sample collection)
- **Weeks 24 and 36 (Doses 8 and 11)**
 - Pre-dose (just prior to the start of infusion)
- **Week 52: (Study Completion/Premature Discontinuation Visit)**
 - May be done at any time during the visit.
- **Week 60: (Post-Treatment Follow-up Visit)**
 - May be done at any time during the visit.

Cohort 2 Subjects:

- **Screening**
 - May be done at any time during the visit.
- **Days 1, 29, 57, 85, and Weeks 24, and 36 (Doses 1, 3, 4, 5, 8, and 11)**
 - Pre-dose (just prior to the start of infusion)
- **Week 52 (Study Completion/Premature Discontinuation Visit)**
 - May be done at any time during the visit.
- **Week 60 (Post-Treatment Follow-up Visit)**
 - May be done at any time during the visit.

Clinical Laboratory Tests

Samples will be obtained at a minimum for the clinical laboratory tests outlined in [Table 6](#) at the time points designated in the [Table 4](#) (Safety and PK Procedures for Cohort 1 and Cohort J1) and Study Activities Table ([Appendix C](#)).

A certified laboratory will be utilized to process and provide results for the clinical laboratory tests. Central Laboratory reference ranges will be provided prior to the initiation of the study. The baseline laboratory test results for clinical assessment for a particular test will be defined as the last measurement prior to the initial dose of study drug.

Table 6. Clinical Laboratory Tests

Hematology	Clinical Chemistry	Urinalysis

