11.5.2 Potentially Clinically Significant ECG Values

Criteria for potentially clinically significant values have been predefined for selected ECG variables as outlined in [Appendix C](#). For each variable, a summary of the number and percentage of subjects in each treatment group who have at least one double-blind observation that meets the PCS criteria and is more extreme than their baseline value will be provided. Listings will also be prepared to include all observations for each variable for each subject that met the PCS criteria for that variable at any time during the study. PCS analysis for ECG values will also be conducted by geographical region. No comparisons of treatment groups will be performed.

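### The by-visit ECG analysis averages or omits every post-infusion ECG, and the SAP does not say whether averaging also precedes the minimum/maximum and PCS analyses

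*SAP*

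**What the plan says.** **ECG schedule (Protocol 5.3.1.1, 12-Lead ECG).** Cohorts 1 and J1 have two ECGs on Day 1: "Pre-dose (just prior to pre-infusion PK sample collection and the start of infusion) and within 15 minutes after the end of infusion". Day 15 has the same pairing: "Pre-dose (just prior to the start of infusion) and within 15 minutes after the end of infusion prior to the PK sample collection". Day 85 is worded almost identically. There is also a single ECG on Day 5, to be timed to match the Day 1 post-infusion collection. Cohort 2 has only pre-dose ECGs on dosing days.

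**Choosing a value for a visit (SAP 6.2).** When a window holds several observations, the one nearest the nominal day is used. Two further sentences follow. For ties: "If two observations have the same distance to the nominal day of the visit, the last non-missing observation will be used in analyses". For the same day: "If more than 1 observation occurs on the same day, the average will be calculated and used in analyses". Neither mentions planned pre-dose and post-infusion pairs.

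**Windows and baseline (SAP 6.2).** Only observations after the first dosing day are assigned to a week. The earliest ECG window is "Week 1 Rx Days 2 through 10 (Cohort 1 and Cohort J1 only". Baseline is the last value before the time of first dosing.

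**Analyses (SAP 11.5.1, 11.5.2 and Appendix C).** Mean change is presented by treatment group for each visit and for the minimum, maximum and final double-blind values. The PCS summary counts subjects with "at least one double-blind observation that meets the PCS criteria" that is also more extreme than baseline. A listing covers every PCS observation at any time in the study. The PCS limits are QTcF > 499 msec and an increase from baseline > 60 msec.

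**The concern.** The post-infusion ECG is the scheduled ECG closest to the end of dosing. Mean Tmax in the single-dose study ranged from 0.3 to 4.6 hours (Protocol 3.0). Protocol 5.6.2 says the extra on-treatment evaluations in Cohorts 1 and J1 are there to detect emerging safety signals promptly. All post-infusion ECGs in the trial come from these two cohorts.

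Applied as written, the SAP's rules give these ECGs no row of their own. Two pairs are blended with a pre-dose value. The third post-infusion ECG, on Day 1, is neither baseline nor any visit, although the Day 5 ECG was timed to match it. An acute shift in mean QTcF, heart rate or another interval would appear at half its size or not at all by visit. A second question is whether the blending also reaches the PCS counts. The SAP leaves that to the programmer.

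**Working it through.** The plan states no figure that depends on this point, so there is none to reproduce. The check maps ECGs to windows, counts them, and works out what averaging does.

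**1. Mapping to the SAP 6.2 ECG windows, with visit tolerances**

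| Cohort 1/J1 ECG | Rx Days | Analysis week |
|---|---|---|
| Day 1 pre-dose | 1 | baseline |
| Day 1 post-infusion | 1 | none |
| Day 5 | 3 to 7 | Week 1 (2 to 10) |
| Day 15, both ECGs | 13 to 17 | Week 2 (11 to 21) |
| Day 85, both ECGs | 81 to 89 | Week 12 (71 to 126) |

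**2. Count**
- Subjects with post-infusion ECGs: 30 + 9 = 39. Share of the planned total: 39/330 = 11.8%.
- Scheduled post-infusion ECGs: 39 × 3 = 117.
- In no visit (Day 1): 39. Averaged with a pre-dose value (Days 15 and 85): 39 × 2 = 78.
- If 1:1:1 holds within the 39, there are 39/3 = 13 per arm and 26 on active drug.

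**3. Effect on by-visit change**

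Reported change = (pre-dose change + post-infusion change)/2. With an assumed pre-dose change of 0, a post-infusion change of +20 msec is reported as +10, and +61 as +30.5.

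Week 2 contains only Cohorts 1 and J1, so the dilution there is one half. Week 12 pools all cohorts by treatment group, and Cohort 2 contributes pre-dose ECGs only. With 13 of 110 subjects per arm contributing pairs and complete data, a +20 msec post-infusion change adds 13 × 10/110 = 1.2 msec to the arm mean.

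**4. Effect on PCS counts, only if averaging is done first**

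Increase criterion: (pre + post)/2 > 60 requires post > 120 − pre.

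| Assumed pre-dose change (msec) | Post-infusion change must exceed (msec) |
|---|---|
| 0 | 120 |
| +10 | 110 |
| +20 | 100 |

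For example, +10 before and +70 after average to +40, which misses the criterion that +70 alone meets.

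Absolute criterion: (pre + post)/2 > 499 requires post > 998 − pre.

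| Assumed pre-dose QTcF (msec) | Post-infusion QTcF must exceed (msec) |
|---|---|
| 400 | 598 |
| 420 | 578 |
| 440 | 558 |

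The pre-dose values are illustrations; the documents give none. If averaging is confined to choosing a visit value, none of the loss in step 4 occurs.

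**The case against.** A reader might infer that no analysis looks at ECGs near peak exposure. The documents do not support that.

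- The minimum and maximum changes (SAP 11.5.1), the PCS count and the any-time PCS listing (SAP 11.5.2) do not depend on windows. SAP 11.1 bounds the double-blind safety period only from above, at 45 days after the last dose. Protocol 8.1.6.4 counts PCS values at any time after the first dose. The Day 1 post-infusion ECG can enter all of these.
- The Day 5 ECG stands alone in Week 1. With the 27 to 37 day half-life in Protocol 3.0 and an assumed mono-exponential decline, concentration four days after dosing is 2^(−4/27) = 90% to 2^(−4/37) = 93% of peak. An early distribution phase would lower this. Effects tied to sustained exposure therefore remain visible.

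A reader might also infer that PCS values will be missed. That depends on an order of operations the SAP does not state. The averaging sentence closes a paragraph about visit windows, and the PCS wording reads naturally as individual values.

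Third, two same-day ECGs are equally far from the nominal day, so the tie sentence would select the later, post-infusion ECG. On that reading Week 2 would consist of post-infusion values, unlabelled and with the pre-dose values dropped. The same-day sentence is the more specific of the two and ordinarily governs, but the conflict is real and could yield different tables from the same data.

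Finally, ECGs are read locally at once, centrally within about 3 business days, and the DMC reviews unblinded safety data. Immediate subject safety does not rest on these tables.

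These points narrow the concern but do not remove it. A maximum does not show when it occurred, and it mixes 39 subjects who have post-infusion ECGs with about 290 who have none. It cannot show a mean post-infusion shift below the PCS limits.

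**Conclusion.** The concern holds for the by-visit analysis. With the same-day sentence applied as written, none of the 117 scheduled post-infusion ECGs is summarised as its own time point: 78 are averaged with a pre-dose value and 39 fall in no visit. A change confined to the post-infusion ECG is halved in Week 2 and diluted further in Week 12. The Day 1 gap comes from the week-assignment rules, not from the averaging sentence.

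For the minimum/maximum and PCS analyses the finding is an ambiguity, not a demonstrated loss. The 120 msec figure applies only if averaging precedes those steps and the pre-dose change is 0.

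The scope is limited: 39 of about 330 subjects, a safety table, and no effect on the primary endpoint. It is still worth correcting, because the stated rule discards a distinction the schedule was built to provide, and the data are already planned.

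**What to change.** Amend SAP 6.2 and 11.5 as follows:

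1. Exempt planned pre-dose and post-infusion ECG pairs from same-day averaging, and say which sentence governs for any other same-day repeats.
2. For Cohorts 1 and J1, summarise change from baseline for pre-dose and post-infusion ECGs as separate time points on Days 15 and 85, and add a Day 1 post-infusion time point.
3. State that the minimum, maximum and PCS analyses use every individual post-baseline ECG, including Day 1 post-infusion, without averaging.

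The cost is a few SAP lines and table rows, with no new visits, ECGs or subjects. The post-infusion summaries will rest on about 13 subjects per arm, so they should be read as descriptive.
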